To ensure quality assurance and intervention fidelity, all moderators will be provided a training of smoking cessation knowledge, and moderating skills to motivate participants to share. Our co-investigator ([name] [name]), who has the experience of using Positive Psychology theories in the FAMILY project, will train the moderators to use specific texts, “emoji” and short videos to express gratitude and appreciation towards participants’ sharing. Also, a research nurse will review the discussion contents, provide service referral for the participants who relapse, and organize case conference with the moderators each month to improve group moderation skills.

The control group will only receive 3 mobile phone text messages each week in the 8 weeks after recruitment. These message contents will be the same as those received by the intervention group. Our intervention will not interrupt the services that all participants will be receiving in the cessation clinics.

Follow-up

All participants will be followed up via telephone by an allocation-blinded interviewer at 3-, 6- and 12-month after the random group allocation. Only the participants who report abstinence in the past 7 days will be invited to provide samples of exhaled breath and/or saliva for biochemical validation at their residence, workplace or nearby, as preferred by the quitters. The Bedfont Smokerlyzer and iScreen OFD Cotinine Saliva Test Kit will be used for validations. To increase participation, the participants will be given HK\$100 (approximately equivalent to US\$12.8) as a compensation for their time cost. All participants will not know the validation incentive at baseline. The validation takes very short time (3 minutes) and is easy.

Allocation concealment

All recruitment staff and participants will be concealed to the group allocation at recruitment. The research staff will open the envelope of group allocation according to the serial number on the envelope, so he/she will not know the group sequence.

Blinding

Participants and group moderators cannot and will not be blinded to the intervention. Assessors of the follow-up outcomes and the research analysts will not be involved in the recruitment and intervention delivery, and will be blinded to the group allocation (single blindness).

Outcomes

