The School of Nursing and the School of Public Health of the University of Hong Kong have good reputation and academic track record in the research and practice of smoking cessation. The project team has been collaborating with the Department of Health, Hong Kong Council on Smoking and Health (COSH), Integrated Centre on Smoking Cessation of Tung Wah Group of Hospitals and other relevant non-governmental organisations to promote smoking cessation. The research team has expertise from different disciplines (e.g. medical doctors, nurses, social workers and statisticians) who have sufficient capacities to organize the training, promotion and vigorous evaluation with various methods. The project team has its own essential equipment including counselling room, computers, telephone, and validation tools for smoking abstinence for the project implementation.

The PA ([name]) is a primary investigator of many randomized trials of examining cutting-edge smoking cessation interventions, who have published numerous journal papers and have been awarded for many smoking cessation trials. His 2 HMRF applications in the 2016 round (as co-A), which are also related to m-health interventions, have obtained ratings “3” and are potentially funded (Project no. 14151111 and 16150752). He has extensive statistical knowledge and experience in manpower management for randomized trials. One of the co-A (CW) has extensive experience in the cost and cost-effectiveness analysis of healthcare interventions in Hong Kong. Another co-A (MC) is an international scholar who has strong track record of publications and grants in the analysis of social media activities with advanced text mining skills.

f) Justification of Requirements:

Total: \$ 967,620

Staff cost - \$ 696,200

1. A full-time Research Assistant II (pt5, RAI) will assist the principal investigator in coordinating all data collection, implementing the whole project, performing data analysis, and preparing reports and all other result dissemination activities. The RA will be moderator of some WhatsApp social groups
 - Total amount = 24 months x \$18,806 per month incl. MPF = \$451,344
2. 5 part-time Research Assistants II, moderators (pt5, RAI): They will be the moderators of the 50 WhatsApp social groups to facilitate discussions and delivering advices to smokers (8 weeks for each group)
 - Hours required = 50 groups x 8 weeks x 2 hours per week = 800 hrs

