 - 800 hours x 112 per hour incl. MPF /5 staff /9 months =\$1991 per staff per month
 - Total amount = \$1991 per month incl. MPF x 5 staff x 9 months = \$89,595
3. A part-time Registered Nurse (pt3, Nurse) with rich experience in smoking cessation:

- design intervention guidelines and the self-help booklet, providing training workshop to the recruitment staff and moderators (40 hrs x 2 months =80hrs)
 - hold case conference with the moderators, recruitment staff and telephone interviewers each month (4 hrs x 19 months =76hrs)
 - 80 hrs + 76 hrs x \$167 per hour incl. MPF /21 months=\$ 1241 per staff per month
 - Total amount = \$1,241 per month incl. MPF x 21 months =\$26,061
4. 10 part-time Student Research Assistants/ Technical Assistants (pt 2, Student RA/TA):
- Recruitment for subjects in clinics (4 hrs x 5 times per week x 30 weeks = 600 hrs)
 - Telephone follow-ups at 6-month and 12-month: 1,008 participants x 15 minutes x 2 follow-ups = 504 hrs;
 - Exhaled carbon monoxide (CO) validation at 6-month and 12-month: 504 intervention group participants x 23% quit rate = 116 participants; 504 control group participants x 15% quit rate = 76 participants, total: 192 quitters x 2 validations x 2 hrs = 768 hrs;
 - Total hours = 600hrs +504 hrs + 768 hrs = 1,872 hours
 - 1,872 hours x \$69 per hour incl. MPF / 10 staff / 19 months = \$680 per staff per month
 - Total amount =\$680 per month incl. MPF x 10 staff x 19 months = \$129,200

General Expenses - \$ 271,420

1. Conference (i.e. Travel and subsistence) (\$10,000)
2. Publication costs (\$20,000)
3. Audit fee (\$5,000)
4. Incentives for participants
Incentives for quitters who complete the exhaled CO validation at the 6-month and 12-month follow-ups: 504 intervention group participants x 23% quit rate = 116 participants; 504 control group participants x 15% quit rate = 76 participants, total: 192 quitters, 192 quitters x 2 validations x \$100 cash incentive = \$38,400
5. Incentives for participants who complete the telephone follow-up (1,008 participants x 2 follow-ups x \$50 supermarket coupon = \$100,800)
6. Incentive for participants who complete the in-depth interview (20 participants x \$300 = \$6,000)
 - Total = \$38,400 + \$100,800 + \$6,000 = \$145,200
7. Production of self-help booklet (1,100 booklets x \$5 = \$5,500)
8. Mobile phones for WhatsApp social group (3 phones x \$1,000 = 3,000)
9. CO monitors and mouthpieces for the validations (3 monitors x \$6000 = \$18,000)

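### The staffing plan does not deliver the stated blinding: a research assistant who performs data analysis also moderates WhatsApp groups, and telephone interviewers are listed in monthly case conferences with the unblinded moderators

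*Combined protocol and SAP*

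**What the plan says.** The Blinding subsection makes two commitments. On roles: "Assessors of the follow-up outcomes and the research analysts will not be involved in the recruitment and intervention delivery". On knowledge of allocation, the same people "will be blinded to the group allocation (single blindness". The Follow-up subsection repeats the second for the calls: "All participants will be followed up via telephone by an allocation-blinded interviewer at 3-, 6- and 12-month". The Blinding subsection also concedes: "Participants and group moderators cannot and will not be blinded to the intervention".

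The staff list in section f) Justification of Requirements assigns the work as follows.

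- Item 1, full-time research assistant, who assists the principal investigator. Duties include coordinating data collection and "performing data analysis, and preparing reports and all other result dissemination activities. The RA will be moderator of some WhatsApp social groups".
- Item 3, part-time nurse, who is to "hold case conference with the moderators, recruitment staff and telephone interviewers each month (4 hrs x 19 months =76hrs". The Interventions subsection describes the nurse's monthly conference as one with the moderators, meant to improve moderation skills. It does not mention interviewers.
- Item 4, a single pool of ten student assistants, funded for recruitment ("Recruitment for subjects in clinics (4 hrs x 5 times per week x 30 weeks = 600 hrs"), for telephone follow-up at 6 and 12 months (504 h) and for CO validation (768 h).

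**The concern.** The participants know their arm, so the plan relies on two protections against biased assessment: biochemical validation, and blinding of the people who assess and analyse. The second is stated without qualification, but the staffing plan gives some of those people roles that conflict with it.

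Validation does not make the primary outcome independent of the interviewer. Only participants who report 7-day abstinence by telephone are invited to give a sample. An interviewer who knows the arm could probe differently, or try harder to arrange the test, without affecting any test result. Self-reported 7-day and continuous abstinence, relapse, smoking urge, withdrawal score and EQ-5D-5L (which feeds the QALYs) have no biochemical check.

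For the analyst, the exposure is to choices left open in the analysis: covariates for the adjusted model, the imputation model for missing CO, and the handling of incomplete validations.

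**Working it through.** The documents give no figure for bias, so the check compares duties and dates.

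**1. Analyst.** The Blinding subsection says analysts have no part in delivery. Item 1 gives one person both data analysis and moderation of some groups. Moderation is the intervention, and only the intervention arm has groups, so this person knows the arm of every member of the groups moderated. The two statements cannot both hold for any outcome analysis this person performs.

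**2. Interviewers.** Item 3 lists interviewers with moderators; the Interventions subsection lists moderators only. A moderator's case is necessarily an intervention-arm participant, so discussing an identifiable one discloses allocation. No safeguard, such as separate sessions or de-identified cases, is described.

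**3. When the exposure could occur.** Inputs: recruitment about 7 months (Setting); groups run 8 weeks, about 2 months (Interventions); calls at 3, 6 and 12 months (Follow-up); part-time moderators funded for 9 months and conferences for 19 months (section f). I assume that the conference months start with recruitment, which fits 7 + 12 = 19.

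| Activity | Months from first recruitment |
|---|---|
| Groups running | 0 to 7 + 2 = 9 |
| 3-month calls | 3 to 7 + 3 = 10 |
| 6-month calls | 6 to 7 + 6 = 13 |
| 12-month calls | 12 to 7 + 12 = 19 |
| Case conferences | 0 to 19 |

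Delivery overlaps the 3-month calls (months 3 to 9) and the 6-month calls (months 6 to 9). The first 12-month call comes 12 − 9 = 3 months after the last group closes. For the last 19 − 9 = 10 conference months no part-time moderator is funded. The full-time assistant, also a moderator, is funded for 24 months.

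**4. Student pool.** 600 + 504 + 768 = 1,872 h, as the plan states. The budget does not say whether the same individuals recruit and assess.

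**5. Is the assistant needed as a moderator?** 50 groups × 8 weeks × 2 h = 800 h, exactly the hours funded for the five part-time moderators. On the plan's own figures, no further moderation time is required.

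**6. Room between self-report and validation.** In the pilot at 6 months, 15% validated out of 39% self-reported in the control arm is 15/39 = 38.5%; for WhatsApp, 26/64 = 40.6%. Most self-reported quitters were not validated, so the step from telephone report to completed test matters. These ratios do not separate people who were not tested from people who failed the test, and they say nothing about interviewer behaviour.

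**The case against.** The strongest reply is that this is a budget justification loosely worded against a clear methods section. Several parts of it have force.

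- The assistant assists the principal investigator and may not be the only analyst. The project also includes text mining, framework analysis and cost-effectiveness work. This stands as a limit: a reader might infer that the sole analyst of the primary outcome is unblinded, and the documents do not say so. But they name no separate blinded analyst either, and the conflict with the Blinding subsection remains.
- Item 3 could list the staff the nurse meets over the project, rather than one joint session. A reader might infer that interviewers will be unblinded. The text shows a route to unblinding, not proof of it. For the primary endpoint an interviewer would usually have to remember individuals from meetings held months before.
- A reader might take the shared student pool as a breach of blinding. It is not shown to be one: ten people can be divided by task, and recruiters are concealed from allocation, so having recruited someone does not reveal the arm. What remains is that separation is promised and not arranged.
- The endpoint is biochemically verified, and multiple imputation of missing CO is planned as a sensitivity analysis. Both help. Neither addresses who is invited to the test.
- The rule counting people as smokers is written for those lost to or refusing follow-up. It does not explicitly cover someone who declines only the test, so it should not be quoted as if it did.

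**Conclusion.** The point holds as an internal conflict: the plan states a blinding that its staffing does not deliver. The analyst part is a direct contradiction between the Blinding subsection and item 1. The interviewer part is an undocumented safeguard plus a disagreement about who attends the conferences; it bears mainly on the 3- and 6-month calls, and on the 12-month call only if the same interviewers continue and carry the knowledge forward. The student pool is a secondary point.

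No size can be given. A reader might set assumed differences in test uptake between arms against the planned effect of 8 points (23.0% against 15.0%) and obtain a bias of several points. The documents supply no such uptake figures, so that result would only reflect the values chosen. The conclusion rests on the written duties, and on the assumption that conferences may discuss identifiable participants, which the plan neither states nor rules out.

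**What to change.** Reconcile the Blinding and Interventions subsections with section f), as follows.

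1. Remove telephone interviewers and CO validators from the moderators' case conferences, as the Interventions subsection already describes, and hold their quality meetings separately.
2. Either take the full-time assistant off moderation, or have the primary analysis done by someone with no part in delivery. In both cases work on coded arms, and lock the primary-analysis code before WhatsApp group identifiers and post counts are merged, because these reveal the arm.
3. Rota the ten student assistants so that recruiters do not assess outcomes.
4. If these steps are not taken, describe the blinding as partial and say which roles are unblinded.

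Cost: a rota change and one short extra meeting a month. Each additional nurse hour per month over 19 months would be 19 × $167 = $3,173 at the budgeted rate, or nothing if the existing 4 hours are divided. Taking the assistant off moderation needs no new funded hours on the plan's own figures.

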relapses occur within the first few weeks of abstinence[19], this can be improved by recruiting quitters who have just quit, and starting the WhatsApp groups as soon as possible. Second, the intervention content and dosage through social media needs to be revised to increase participation. For instance, only 6 out of the 16 participants, who reported relapse at 2-month, shared their relapse experience in the group. The few number of reports of relapse posed barriers for early intervention. Due to limited number of eligible participants, some groups had only 2 to 5 participants, which led to inactive discussion. About one-fourth of the participants only stayed in the group, but did not post anything. These findings highlighted the importance of skilful and theory-driven group moderation, and inclusion of more updated and interesting content to increase the level of participation. Lastly, for a larger RCT, we shall add more recruitment sites to increase participant recruitment and generalizability. A subsequent cost-effectiveness analysis based on trial data will establish the optimal balance between costs and health effectiveness outcomes, and provide health economic data to policymakers to facilitate informed decision-making of health interventions for tobacco control

c) Aims and Hypotheses to be Tested:

This study aims to examine the effectiveness and cost-effectiveness of WhatsApp group discussion for smoking relapse prevention. To assess the effect due to treatment modality through the WhatsApp social group, we will analyse the frequency and topics of the posts in each social group and in each participant. The primary hypothesis is whether quitters who participate in the WhatsApp group discussion will have a higher prevalence of validated tobacco abstinence at 12-month follow-up than those who do not. Our second hypothesis is that greater participation in the social groups, indicated by number of posts received, posted and/or viewed, was associated with higher likelihood to quit at 12-month. The third hypothesis is that the WhatsApp intervention for a recent quitter is a more cost-effective option for tobacco abstinence and prolonged survival when compared to the control group.

d) Plan of Investigation:

(i) Subjects

Inclusion criteria:

- Smoke at least 1 cigarette per day at the service intake
- Aged 18 years or above
- Have enrolled or re-enrolled in the smoking cessation treatment for no more than 8 weeks
- No smoking for 7 to 14 days

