Simple individual randomization by sequentially numbered, opaque sealed envelopes (SNOSE) will be used to ensure the recruitment staff and the participants will be concealed to the allocation sequence before the group allocation. The principal investigator will prepare about 1,100 identical, opaque, sealed, A5-sized envelopes, with a unique 3-digit serial number on the cover of each envelope as an identifier. Half of them will contain a card indicating the intervention group, and the others will contain a card indicating the control group. When a participant is recruited, the research staff will open 1 envelope according the serial number to allocate the recruited participant, according to the card inside.

Interventions

When the research staff collects 10 participants in the intervention group (a few groups will have 11 participants), probably within one week, he/she will set up the WhatsApp group with them. Each WhatsApp group (about 50 groups in total) will allow real-time group discussion for 8 weeks. They will receive each week at least 3 text messages or videos from a moderator, which will be based on the six approaches delineated in “Treatments for the Recent Quitter” of the US Clinical Practice Guidelines on Treating Tobacco Use and Dependence[18]. Based on the Positive Psychology theories[20], and our experience of the FAMILY project, we developed a framework of four principles to enhance the online group moderation: (1) Using active listening skills to understand the thoughts and feelings behind participants’ sharing; (2) Showing sincere,

immediate, specific, and concrete appreciation and gratitude towards their sharing; (3) Mindful awareness of the group dynamics and giving strategic reactions; (4) Enhancement of self-efficacy, sense of control and satisfaction among the participants. In addition, if any participant shares their relapse experience in the group, the moderator will engage other participants to provide appreciation and support, or, if preferred, actively refer him/her to existing cessation services.

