The primary outcome is biochemically validated (exhaled carbon monoxide < 4ppm; or/and saliva cotinine < 10ng/ml) tobacco abstinence at 12-month follow-up, which have been confirmed as a stringent criterion for abstinence verification for quitters who use nicotine replacement therapy^[21]. Secondary outcomes include prevalence of self-reported 7-day and continuous abstinence over the study period, and relapse rate, which is defined as the proportion of quitters who smoke at least 5 cigarettes in 3 consecutive days over the study period. Ancillary outcomes include change in frequency and intensity of smoking urge, change in the Minnesota Nicotine Withdrawal Scale (MNWS), and the change in HRQOL measured by Short-form 6-item instrument and EuroQoL 5-dimension 5-level (EQ-5D-5L) health utility scores from baseline to follow-ups. For cost-effectiveness analysis, the outcomes are the incremental cost-effectiveness ratio (ICER) in terms of cost per an additional tobacco abstinence gained for intervention compared to control group, and the ICER in terms of cost per life-years gain or quality-adjusted life-years gained for intervention versus control group.

(iii) Study design A pragmatic open-labelled 2-arm randomized controlled trial

(iv) Data processing and analysis

Statistical analysis

By intention-to-treat analysis (in line with CONSORT guideline), participants who are lost or refuse the follow-up will be treated as smokers with no changes in daily cigarette consumption. The analysis with multiple imputation (MI) procedure to impute the missing exhaled CO will be conducted as sensitivity analysis. Considering the correlated outcomes of participants within the same WhatsApp group, a post-hoc analysis by generalized estimating equation (GEE) model will be used to summarise the intervention effect with the odds ratios, with and without adjustment for baseline characteristics. Number needed to treat (NNT), which shows the number of treated subjects needed to have one additional quitter at 12-month, will be computed by taking the reciprocal of the risk difference between the 2 RCT groups. Number of posts received, posted or/and viewed in each participant and in each social group will be documented, and then included in the final GEE model to assess their association with the cessation outcome.

Text mining of the WhatsApp groups

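### The analyst-blinding statement has no limit of stage or analysis, but it lapses once the planned GEE uses real WhatsApp-group membership, and the staffing plan contradicts it

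*Combined protocol and SAP*

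**What the plan says.** The Blinding section under Methods makes two statements. On roles: "Assessors of the follow-up outcomes and the research analysts will not be involved in the recruitment and intervention delivery". On knowledge of allocation: they are outside delivery "and will be blinded to the group allocation (single blindness"). Neither is restricted to a stage of the work or to particular analyses. The same section says that participants and moderators cannot be blinded.

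The Statistical analysis section names one regression for the intervention effect: "Considering the correlated outcomes of participants within the same WhatsApp group, a post-hoc analysis by generalized estimating equation (GEE) model will be used". Odds ratios are to be given "with and without adjustment for baseline characteristics", and no covariates are listed. Posts received, posted or viewed are documented "and then included in the final GEE model to assess their association with the cessation outcome".

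The Interventions section shows that the clusters belong to one arm. A WhatsApp group is set up when the staff member "collects 10 participants in the intervention group (a few groups will have 11 participants"), giving about 50 groups. In the other arm: "The control group will only receive 3 mobile phone text messages each week in the 8 weeks after recruitment".

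The Justification of Requirements lists data analysis among the duties of the full-time research assistant, and says that the same person will moderate some of the groups.

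**The concern.** The trial is open-label, so blinded analysis is one of the few safeguards it can claim, together with blinded telephone assessment and biochemical validation. A reader would take the sentence to mean that every analysis choice was made without knowledge of the arms. Two parts of the plan conflict with that.

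- **Data structure.** A file that carries real WhatsApp-group membership shows who was in the intervention arm. Relabelling the arms A and B does not help, because the arm with groups is the WhatsApp arm.
- **Staffing.** A person who moderates groups knows the allocation of the people in them and is part of delivery. The plan gives that person analysis work.

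This matters because choices are still open when the arms become visible. The analysis section does not name a primary test, calls the GEE post-hoc, lists no covariates, and does not say whether the adjusted or the unadjusted estimate is primary.

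**Working it through.** **The plan's own figure.** From Sample size calculation: 23.0% versus 15.0%, two-tailed z-test, 5% level, 90% power. With mean proportion 0.19, n per arm = [1.96 × √(2 × 0.19 × 0.81) + 1.2816 × √(0.23 × 0.77 + 0.15 × 0.85)]² / 0.08² = (1.0874 + 0.7073)² / 0.0064 = 503.3, rounded up to 504 per arm and 1,008 in total. The stated figure is reproduced. This test uses only the outcome and an arm label.

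**Cluster layout.** Place 504 people in 50 groups of 10 or 11. The number of groups of 11 is 504 − 50 × 10 = 4, which leaves 46 groups of 10 (46 × 10 + 4 × 11 = 504). Controls have no groups. The plan does not say how they enter the GEE; assume clusters of one. Every cluster larger than one is then in the intervention arm and every cluster of one is a control, so cluster size classifies 504 + 504 = 1,008 of 1,008 participants correctly.

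**What each planned analysis reveals:**

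- Two-proportion comparison, risk difference and number needed to treat: a coded arm label is enough, so blinding can be kept.
- GEE on actual group membership: allocation is visible unless controls are given dummy groups, which the plan does not describe.
- GEE with post counts: allocation is visible, since controls have no group in which to post or view. This addresses the second hypothesis ("Our second hypothesis is that greater participation in the social groups, indicated by number of posts received, posted and/or viewed"), where arm blinding is not at issue.

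**Roles side by side.** The Blinding section says that analysts are not involved in delivery. The Justification of Requirements has the full-time research assistant doing both. Both cannot be true of that person.

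**Illustration of what open choices could do.** Suppose an analyst who knows the arms reports whichever of k versions of the primary analysis most favours the intervention, with test statistics that share a common correlation ρ. With no true effect, the chance that at least one version is significant in favour of the intervention is 1 − ∫ φ(u) × Φ[(1.96 − √ρ × u) / √(1 − ρ)]^k du. The results are:

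- k = 1: 2.5%
- k = 2: 3.2% (ρ = 0.95) and 3.9% (ρ = 0.8)
- k = 4: 4.0% (ρ = 0.95) and 5.7% (ρ = 0.8)

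The values of k and ρ are assumptions; the documents give no source for either.

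**The case against.** The strongest reply is that this is an undescribed procedure and not a failed design. Nothing in the plan requires group identifiers or post counts to be in the file while outcomes and missing data are coded, or while the arms are compared. A GEE on clusters alone could be masked with dummy group labels for controls. A reader might infer that analyst blinding is impossible in this trial, and the documents do not support that. This part of the reply stands.

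The consequences are also limited. The primary outcome is biochemically validated, interviewers are blinded, and participants lost to follow-up count as smokers. Multiple imputation is a sensitivity analysis, so its open specification does not create another version of the primary analysis. Both adjusted and unadjusted estimates are planned, so reporting only one would depart from the plan. This stands too, but the unnamed covariates and the unstated primary test remain open.

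A further reply is that the real weakness is pre-specification, because an analyst working with labels A and B could also try several models. That is largely right, and it is why the fix locks the analysis as well as correcting the sentence. It does not make the sentence true.

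A reader might also infer that the 5% error rate rises to between 6.5% and 11.4%. Those values count significance of any version in either direction. They do not describe choosing the version that favours the intervention, for which the range is 3.2% to 5.7% against 2.5%.

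No part of the reply answers the staffing conflict.

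**Conclusion.** The concern holds in a limited form. The unlimited statement of analyst blinding cannot be kept once the GEE is fitted on actual WhatsApp-group membership, and no masking procedure is described. If controls enter as clusters of one, allocation is revealed for all 1,008 participants. Separately, the Blinding section and the staffing justification contradict each other about the full-time research assistant.

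The documents do not show that blinding is unattainable for the simple between-arm comparison, that the post counts compromise the primary result, or that any selection of models will occur. The rise in false positives favouring the intervention, from 2.5% to about 3.2% to 5.7%, is only an illustration under 2 to 4 assumed versions with correlation 0.8 to 0.95. The sample size is unaffected. The plan should be changed because it claims a safeguard that it does not deliver as written.

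**What to change.** Replace the unlimited claim in the Blinding section with a two-stage rule.

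1. **Blinded stage.** Lock the outcome coding, missing-data coding, primary test, covariate list and analysis code on a file without arm names, group ID or posts. Test the code with dummy group labels given to both arms. State how controls enter the GEE.
2. **Unblinded stage.** Merge group ID and post counts, run the locked code, and report any later change as made after unblinding.

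Reconcile the Blinding section with the Justification of Requirements by assigning the primary analysis to a team member who does not moderate groups. If that cannot be arranged, drop the statement that analysts are blinded.

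The cost is protocol and SAP wording, an ordered data merge and a clear division of duties. Sample size, follow-up and intervention do not change. The downside is that the blinding the trial can claim becomes less broad.
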